## 6.2 Description of Other Study Products

The Philips HeartStart Monitor/Defibrillator can be used with the following accessories for this study. NOTE: None of the defibrillator accessories will be available for this study.

Model No.	Product Name/Description	UDI GTIN
M2202A	Adult radiotranslucent foam solid gel electrodes, 5 electrodes/pouch (300/case)	20884838002535
989803148821	Small Adult radiolucent foam, solid gel ECG electrode, 30 electrodes/pouch (600/case)	20884838007783
M1644A	5-lead ICU ECG set, snap, limb (AAMI)	00884838021280
M1645A	5-lead ICU ECG set, snap, limb (IEC)	00884838010833
M1602A	5-lead ICU ECG set, snap, chest (AAMI)	00884838021259
M1668A	5-lead ECG trunk cable (AAMI/IEC)	00884838010963
989803173131	5-lead ECG set, disposable, bedside (AAMI) (1 pack=20 lead sets)	20884838075690
989803174211	5-lead ECG set, disposable, bedside (IEC) (1 pack=20 lead sets)	20884838075737
M1663A	10-lead (5+5) ECG trunk cable, 2.0m (AAMI/IEC)	00884838010925
M1949A	10-lead (5+5) ECG trunk cable, 2.7m (AAMI/IEC)	00884838002463
989803176161	5-lead ruggedized ECG cable, snap, limb (AAMI)	00884838028302
989803176171	5-lead ruggedized ECG cable, snap, chest (AAMI)	00884838028319
989803176181	5-lead ruggedized ECG cable, snap, limb (IEC)	00884838028326
989803138171	75mm Chemical Thermal Paper (10 rolls)	10884838000725
989803202611	USB Data Drive	00884838087477
989803202921	Wireless Communication Module	00884838090958
989803202601	Rechargeable Lithium-Ion battery pack. Discontinue after 989803206451 release.	00884838087491

Document ID:	CC_TC_ECR_Intrepid 12Lead_2022_11549	Document title: Philips HeartStart Intrepid 12-lead ECG Study – The ICE study Protocol	Classification:	For internal use
Modified:	12SEP2022		Author:	[name]
Version:	2.0		Approver:	Ref to Page 2
Status:	Final		Page:	28 of 51
		Clinical Protocol		

Model No.	Product Name/Description	UDI GTIN
989803206451	Rechargeable Lithium-Ion battery pack. Replace 989803202601. For Rest of World. Not release for India.	00884838099197
989803202931	DC Power Module	00884838093669
M3725A	Test Load, 50 Ohm, plug-style	00884838033573
989803171271	Test Plug, shorted	20884838015405
SpO2 Sensors and Cables		
M1131A	Single-patient SpO 2 Sensor - Pediatric/Adult Finger (0.5m)	00884838010246
M1132A	Infant Single-Patient SpO 2 Sensor – Infant finger (0.9m)	00884838010284
M1133A	Neo/Infant/Adult Single-Patient SpO 2 Sensor – Adult Finger, Infant Thumb/Toe (0.9m)	00884838010215
M1134A	Adhesive-free Neo/Inf/Adult SpO 2 Sensor - Neonatal foot/hand; Infant thumb/great toe; Adult finger (0.9m)	00884838010222
M1191B	Reusable SpO 2 Sensor - Adult Finger (2m)	00884838010215
M1191BL	Reusable SpO 2 Sensor - Adult Finger (3m)	00884838010222
M1192A	Reusable SpO 2 Glove Sensor – Pediatric/Small Adult (1.5m)	00884838010246
M1196A	Reusable SpO 2 Sensor - Adult Finger (3m)	0084838001381
M1941A	SpO 2 Extension Cable, (2m)	00884838011922
M1943A	Reusable SpO 2 Sensor Adapter Cable (1m)	00884838011939
M1943AL	Reusable SpO 2 Sensor Adapter Cable (3m)	00884838011946
Non-Invasive Blood Pressure Cuffs and Air Hoses - NBP Air Hoses		
M1598B	NIBP Adult/Pediatric Air Hose (1.5 m)	00884838001695

Document ID:	CC_TC_ECR_Intrepid 12Lead_2022_11549	Document title: Philips HeartStart Intrepid 12-lead ECG Study – The ICE study Protocol	Classification:	For internal use
Modified:	12SEP2022		Author:	[name]
Version:	2.0		Approver:	Ref to Page 2
Status:	Final		Page:	29 of 51
Clinical Protocol				

Model No.	Product Name/Description	UDI GTIN
Non-Invasive Blood Pressure Cuffs and Air Hoses - Multi-Patient Comfort Care Cuffs - Single Hose		
M1572A	Comfort Care Cuff - Pediatric	00884838001558
M1573A	Comfort Care Cuff - Small Adult	00884838001565
M1574A	Comfort Care Cuff - Adult	00884838001572
M1574XL	Comfort Care Cuff – Adult XL	00884838050075
M1575A	Comfort Care Cuff - Large Adult	00884838001589
Non-Invasive Blood Pressure Cuffs and Air Hoses - Multi-Patient Easy Care Cuffs - Single Hose		
M4552B	Easy Care Cuff – Infant (Antimicrobial, Qty 1)	00884838002999
M4553B	Easy Care Cuff – Pediatric (Antimicrobial, Qty 1)	00884838003026
M4554B	Easy Care Cuff - Small Adult (Antimicrobial, Qty 1)	00884838003057
M4555B	Easy Care Cuff – Adult (Antimicrobial, Qty 1)	00884838003095
M4556B	Easy Care Cuff - Adult Long (Antimicrobial, Qty 1)	00884838003125
M4557B	Easy Care Cuff - Large Adult (Antimicrobial, Qty 1)	00884838003156
M4558B	Easy Care Cuff - Large Adult X-Long (Antimicrobial, Qty 1)	00884838003187

### 6.3 Concomitant Therapy

There are no medication/therapy restrictions in the inclusion/exclusion criteria. Participants may continue to use any current medications/therapies required.

Document ID:	CC_TC_ECR_Intrepid 12Lead_2022_11549	Document title: Philips HeartStart Intrepid 12-lead ECG Study – The ICE study Protocol  Clinical Protocol	Classification:	For internal use
Modified:	12SEP2022		Author:	[name]
Version:	2.0		Approver:	Ref to Page 2
Status:	Final		Page:	30 of 51

## 6.4 Preparation, Handling, Storage, and Accountability

### 6.4.1 Acquisition and Accountability

The HeartStart Intrepid Monitor/Defibrillator and necessary accessories will be shipped to the investigator. The HeartStart Intrepid devices will be returned to the Sponsor at the end of the study. The unused accessories and re-usable used accessories will be returned to the sponsor, any used disposable accessories will be disposed of by the site after use. An inventory of devices will be maintained.

### 6.4.2 Formulation, Appearance, Packaging, and Labeling

The Device Label, User Manual and Operating Manual are included with the IRB submission. Some content of these documents may change before regulatory submission. The Philips HeartStart Defibrillator monitor will be labeled with "CAUTION - Investigational device. Limited by Federal (or United States) law to investigational use."

### 6.4.3 Product Storage and Stability

Allow for settling time if the device has been in extreme temperatures. The time required for the device to warm from -20°C before use is 80 minutes. The time required for the device to cool from 70°C before use is 80 minutes.

### 6.4.4 Preparation

The Philips HeartStart Intrepid Monitor/Defibrillator will be set up by a trained Philips Employee. The staff will be trained to use the ECG monitoring, 12-lead ECG, SpO2, NBP, and data management functions. Proper skin preparation and electrode placement are important elements in producing a high quality 12-Lead ECG. See Appendix A for the *Improving ECG Quality* Application Note.

The study staff will follow the product labeling regarding cleaning and disinfection of the Intrepid Monitor/Defibrillator and the accessories between each participant. See Appendix B for Instructions for Use. Each day prior to seeing participants, the site will ensure the device is ready for use by utilizing the 'RFU' indicator. See Appendix B for *Instructions for Use*.

At the beginning of each week of enrollment (except for the first training week) the study site will complete the operational check per the Instructions for use prior to any participant use.

Document ID:	CC_TC_ECR_Intrepid 12Lead_2022_11549	Document title: Philips HeartStart Intrepid 12-lead ECG Study – The ICE study Protocol	Classification:	For internal use
Modified:	12SEP2022	Clinical Protocol	Author:	[name]
Version:	2.0		Approver:	Ref to Page 2
Status:	Final		Page:	31 of 51

## 6.5 Measures to Minimize Bias

### 6.5.1 Type of Randomization

Block randomization will be employed to ensure balance across subjects with regard to electrode age (new, 24 hours, 30 days).

### 6.5.2 Implementation of Randomization

The randomization schedule will be incorporated into the database. Assignment to an electrode will be apparent upon subject enrollment and entry into the database.

## 7. STUDY PROCEDURES

### 7.1 Recruitment Procedures

#### 7.1.1 Pre-screening

Participants will be contacted by designated study staff from the site's database of patients. Potential participants may also be found by utilizing advertisements.

##### Phone screening

Recruitment will be the responsibility of the site. Potential participants will be screened over the phone for eligibility, and then scheduled for an enrollment visit.

Phone screening will include questions regarding age, sex, height and weight (for calculation of BMI), to facilitate the recruitment of participants of all ages with a wide BMI range.

A waiver of informed consent for screening will be submitted to the IRB for contacting these participants.

#### 7.1.2 Consent

Informed consent is a process that is initiated prior to the individual's agreeing to participate in the study and continues throughout the individual's study participation. Consent forms will be IRB-approved, and the participant will be provided ample time to review the form prior to enrollment, including the opportunity to discuss potential enrollment with family or others. For any participants under the age of 16, a parent will be asked to sign an Informed Consent Form on behalf of their child.

During the phone screening a preliminary assessment of eligibility will be performed by the investigator or designee. Once the participant arrives on site, the investigator or designee will describe the purpose of the study, all study procedures, possible risks of participation, and their rights as a research participant. Participants must be informed that participation is voluntary and

Document ID:	CC_TC_ECR_Intrepid 12Lead_2022_11549	Document title: Philips HeartStart Intrepid 12-lead ECG Study – The ICE study Protocol	Classification:	For internal use
Modified:	12SEP2022	Clinical Protocol	Author:	[name]
Version:	2.0		Approver:	Ref to Page 2
Status:	Final		Page:	32 of 51

they may withdraw from the study at any time without prejudice, and the quality of their medical care will not be impacted by declining to enroll or withdrawing from the study for any reason. After an opportunity to ask questions, willing and eligible participants will be asked to sign the consent form on paper. It is anticipated that the consent process will take approximately 15 minutes to complete. Apart from preliminary eligibility assessment, no study procedures will take place prior to consent.

## 7.2 Study Visits

### Study Visit 1

Once the participant arrives, the study will be explained in full detail. If the participant agrees, he/she will be consented into the study and the participant will be given a copy of the informed consent.

Once consent is obtained the following study related procedures will be conducted:

Demographics: gender, age, ethnicity, height and weight will be collected.

Inclusion/Exclusion Verification

Skin pigmentation assessment: Skin pigmentation will be assessed with a Mexameter probe (C&K Electronic; Köln, Germany) a small hand-held tool held over the skin of the inner arm (an area with minimal sun exposure) for a few seconds that emits three light wavelengths to calculate melanin and hemoglobin content in arbitrary units on a scale of 0-999 (within  $\pm 5\%$ ).

Skin assessment: The participants skin will be assessed with palpation to assess temperature, moisture, and texture.

[figure not shown]
Medical History: Participants will be asked if they have any relevant cardiac history (for example, a pacemaker).

Enrollment into study: Once the above procedures are complete. Participants will be randomly assigned (like the flip of a coin) to a set of ECG electrodes: brand new, package open for 24 hours and package open for 30 days

12-lead ECG: Participants will have 10 electrodes placed on their body by a trained member of the study staff. The electrodes will be placed similar to those used for out of hospital 12-lead ECGs. One electrode is placed on the right shoulder, left shoulder, right waist, and left waist. Six V/C electrodes are placed on the chest. The right waist electrode is the reference electrode, as shown in the figure below. The study team shall use the 'Improving ECG quality' application note for obtaining a good quality ECG. Once the skin is prepped, all of the electrodes will be placed on the patient. The cables will be connected to the electrodes in the following order 3 leads, 5 leads, and chest leads. Once the 5 leads are place and prior to the acquisition of the 12-lead

Document ID:	CC_TC_ECR_Intrepid 12Lead_2022_11549	Document title: Philips HeartStart Intrepid 12-lead ECG Study – The ICE study Protocol	Classification:	For internal use
Modified:	12SEP2022	Clinical Protocol	Author:	[name]
Version:	2.0		Approver:	Ref to Page 2
Status:	Final		Page:	33 of 51

ECG, the 12-lead ECG preview screen will be made available, the study staff will then place the remaining electrodes and determine if a 12-lead ECG can be obtained. If the 12-lead ECG cannot be obtained and the participant has been randomized to either the 1 day or 30 day electrodes, the electrodes will be swapped for electrodes from an unopened package. If the 12-lead ECG cannot be obtained after the electrodes have been changed, this will be considered a 'Fail.'

Source: Derek R. Cooney: Cooney's EMS Medicine: www.accessemergencymedicine.com Copyright © McGraw-Hill Education. All rights reserved.

After the ECG electrodes are placed, the patient will have their SpO2 and noninvasive blood pressure monitored as detailed in the instructions for use. The blood pressure cuff will be placed on the opposite arm from the SpO2 sensor.

Once all electrodes and monitoring functionality is placed, the patient will be given time to relax. Once relaxed, the participant will be asked to lay quietly for up to 15 minutes while the device collects the ECG and other vitals are monitored. See the table below for frequency. After the readings are completed, all equipment will be removed and the participant will be free to leave the laboratory.

Data Acquisition frequency.

Monitoring Functionality	Data Acquisition by device
Non-Invasive Blood Pressure	Minute 0, Minute 5, and Minute 10
12-Lead ECG	Immediately after the NBP cuff deflates (approximately minute 1, minute 6 and minute 11)
SpO 2	Continuously (1 minute intervals)

It is anticipated for the first 1 to 3 participants, that a Philips Engineer and members of the Philips Clinical Team will be on-site to observe the study. The Philips Engineer will be able to troubleshoot any of the issues experienced with the capture of the 12-lead ECG on the HeartStart Intrepid.

Document ID:	CC_TC_ECR_Intrepid 12Lead_2022_11549	Document title: Philips HeartStart Intrepid 12-lead ECG Study – The ICE study Protocol	Classification:	For internal use
Modified:	12SEP2022		Author:	[name]
Version:	2.0	Clinical Protocol	Approver:	Ref to Page 2
Status:	Final		Page:	34 of 51

At the end of each day the device data will be downloaded utilizing the USB drive. This data will be uploaded into the corresponding participant file for analysis. Printed copies of the 12-lead ECG will be stored in the participant file. Once the study is complete, the original paper files will be sent to the sponsor. Copies of the originals will be maintained at the site.

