The Philips HeartStart Intrepid Monitor /Defibrillator is currently released for sale in the European market. It will be submitted to the FDA for 510(k) clearance during the time of this study. In the United States it is considered a Class II medical device. For the purposes of this study, the device will only be able to be used for monitoring and no clinical decision will be made based on the results obtained. None of the defibrillator accessories will be available for use. The Philips HeartStart Intrepid Monitor /Defibrillator used for this study is considered an investigational medical device. The sponsor considers this study to be a minimal risk study with a non-significant risk device. As monitor/defibrillator is not implantable, not supporting or sustaining life, not curing, mitigating, or treating disease, or otherwise preventing impairment of human health, and does not otherwise presents a potential for serious risk to the health, safety, or welfare of a subject.

A 12-lead ECG will be acquired three times (3) for each participant. The 12-lead ECG does not continuously record. As the leads are connected to the electrodes, markers will be placed for the three-lead and five-lead configurations. The Philips HeartStart Intrepid Monitor /Defibrillator has a 12-lead ECG preview screen that will allow the site staff to determine if a 12-lead ECG can be acquired. Once the 'start acquire' button is pushed, the recording will start and approximately 10 to 12 seconds a 12-lead ECG will be recorded. If the 12-lead does not have a good signal, no recording will be able to be obtained.

Participants will be randomized to electrodes that are either from an unopened package or have had the package open for 24 hours or 30 days. The 30-day electrodes will have a window of being opened plus or minus 10 days. The length of time the package is open is proportional to the amount of conductive gel that has dried on the electrode. The longer the electrode package is open, the drier the conductive gel and the higher the impedance. The dried electrodes will be used to simulate high impedance.

Document ID:	CC_TC_ECR_Intrepid 12Lead_2022_11549	Document title: Philips HeartStart Intrepid 12-lead ECG Study – The ICE study Protocol	Classification:	For internal use
Modified:	12SEP2022	Clinical Protocol	Author:	[name]
Version:	2.0		Approver:	Ref to Page 2
Status:	Final		Page:	27 of 51

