### 10.1 Sample Size Determination

Each hypothesized endpoint estimates a target proportion of 99% with an expectation to be statistically better than 90%. Using a one-sided exact test, with 80% power and alpha of 0.025, a sample size of 56 evaluable subjects is required.

Both hypothesized endpoints must be met for study success, therefore alpha level adjustments are not necessary to address familywise error.

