### 10.4.2 Analysis of the Primary Endpoints

Endpoint 1A: Obtaining the 12-lead ECG

Endpoint 1B: Diagnostic quality of the 12-lead ECG tracings

A one-sided exact binomial test will be used to assess each of the primary endpoints. Both endpoints must be met for study success.

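### Electrode age is assigned and visible before skin preparation, so preparation could be adapted to dried electrodes; the exposure is mainly for endpoint 1B

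*Combined protocol and SAP*

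**What the plan says.** Section 7.2 lists demographics, eligibility verification, the skin assessments and cardiac history. Once these are complete, "Participants will be randomly assigned (like the flip of a coin) to a set of ECG electrodes": new, open for 24 hours, or open for 30 days. Skin preparation first appears in the next step, the 12-lead ECG: "Once the skin is prepped, all of the electrodes will be placed on the patient". Staff are told to use the 'Improving ECG quality' application note (Appendix A) to get a good tracing.

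On visibility, Section 6.5.2 says: "Assignment to an electrode will be apparent upon subject enrollment and entry into the database". Section 6.5, on measures to minimize bias, contains only block randomization by electrode age and its implementation.

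Two further statements connect preparation to the purpose of the study. Section 6.1 says: "The dried electrodes will be used to simulate high impedance". Section 6.4.4 says: "Proper skin preparation and electrode placement are important elements in producing a high quality 12-Lead ECG".

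Section 7.2 also has a swap rule. If no 12-lead ECG can be obtained with a 24-hour or 30-day set, the set is replaced from an unopened package. A 'Fail' is counted only if that attempt also fails.

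**The concern.** Dried electrodes are the only means by which the study creates high impedance on purpose. Section 5.1 also names wet skin as a cause, but skin condition is only assessed, not manipulated. By the protocol's own account, skin preparation affects ECG quality. In the order described, the person preparing the skin can already know that the electrodes are dry and has been told to aim for a good tracing. More thorough preparation in those participants would partly undo the challenge, in the participants meant to test the software change.

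Such a performance bias would run towards success. The planned analysis would not reveal it: Sections 10.4.4 and 10.4.5 plan no exploratory or sensitivity analyses, and the body text asks for no record of the preparation done.

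**Working it through.** **Step 1: the plan's own figure.** Section 10.1 states: "Using a one-sided exact test, with 80% power and alpha of 0.025, a sample size of 56 evaluable subjects is required", for a true proportion of 99% against 90%. Section 10.4.2 names the test: "A one-sided exact binomial test will be used to assess each of the primary endpoints".

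With n = 56, the test passes with at most f failures, where f is the largest number with P(failures ≤ f | failure rate 0.10) ≤ 0.025.

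- f = 1: 0.90^56 + 56 × 0.10 × 0.90^55 = 0.0198, which meets 0.025.
- f = 2: 0.072, which does not.
- Power at a true rate of 99%: 0.99^56 + 56 × 0.01 × 0.99^55 = 0.892 per endpoint.

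The smallest n with at least 80% power is 54 (alpha 0.0237, power 0.898), so 56 is adequate. The sample size is not in question. What matters here is that success needs at least 55 of 56, so a few rescued participants could change the result.

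**Step 2: when the age is known.** Section 5.4 counts a participant as enrolled at consent, while Section 7.2 places enrollment just before randomization. On either reading the assignment can be seen before the step in which skin preparation is described. The Schedule of Activities (1.3) gives enrollment to the investigator or designee and data collection to the coordinator. The two may be different people, but nothing withholds the age from the second. The swap rule requires staff to know the age by the time they judge whether an ECG can be obtained. It does not require them to know it before preparing the skin.

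**Step 3: which endpoint is exposed.** For 1A, let d be the chance that a 30-day set fails to give an ECG and s the chance that the replacement set then also fails. A counted failure has probability d × s.

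- If unopened electrodes never fail (s = 0), no 30-day participant can count as a failure, whatever the preparation.
- If s = 0.20 (assumed) and d = 15%, 10% or 5%, the counted failure rate is 3%, 2% or 1%. P(at most 1 failure in 19) is then 0.890, 0.945 or 0.985.

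For 1B, Section 7.4 requires every part of the waveform in every lead to be readable. The swap is triggered only when no ECG can be obtained, so a tracing that is obtained but partly unreadable stays in as a failure. Preparation could matter there.

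**Step 4: illustration for 1B only.** The assumptions, none of which the documents give, are:

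- 1:1:1 allocation, so about 19 of 56 participants on 30-day electrodes (the ratio is not stated);
- one result per participant, although three ECGs are taken;
- no failures among the other 37;
- true 30-day diagnostic-quality rates q of 85%, 90% and 95%.

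P(pass) = q^19 + 19 × (1 − q) × q^18:

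| q | No failure | One failure | P(pass) | P(pass) if the other 37 are at 99% |
|---|---|---|---|---|
| 85% | 0.046 | 0.153 | 0.198 | 0.15 |
| 90% | 0.135 | 0.285 | 0.420 | 0.32 |
| 95% | 0.377 | 0.377 | 0.755 | 0.62 |

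The last column is 0.99^37 × P(at most 1 failure in 19) + 37 × 0.01 × 0.99^36 × q^19. The rows show how sensitive the rule is to a lift in q. They do not estimate any such lift.

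**The case against.** The strongest reply is that the mechanism is conjecture. Nothing in the documents says that preparation effort varies with the operator or that staff would work harder with dried electrodes. Every participant is to be prepared using the same application note, by trained staff. If that note sets fixed steps, little discretion is left. Its content is not in the text available here, so this cannot be settled. The reply stands to this extent: the documents show an opportunity for bias, not its occurrence or size.

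The swap rule is the second reply. A reader might infer that the pass probabilities in Step 4 apply to 1A as well as 1B. They do not: if new electrodes never fail, the swap rescues every failed 30-day set, and even with one in five swaps failing the shift is only from 0.890 to 0.985. Section 6.1 adds that no recording is obtained without a good signal, so some poor-signal cases will go to the swap and never become 1B failures. That tempers the 1B illustration too, but does not cover tracings obtained with unreadable parts.

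A reader might also infer that uneven preparation would blur a comparison between electrode ages. No such comparison is planned: both primary tests set one pooled proportion against 90%, and electrode age is only balanced by blocks.

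Finally, reordering is a partial remedy. Staff will still know the age when they place the electrodes and judge the preview screen. This is true, but it is no reason to leave the preparation route open when closing it costs so little.

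**Conclusion.** The point holds as a modest, avoidable risk of performance bias. The sequence and the visibility of the assignment are documented. The body text contains neither concealment until preparation is done nor a requirement for equal preparation across electrode ages. If preparation did differ in the way described, it would weaken the high-impedance challenge and bias the results towards success, mainly in 1B.

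Its size is unknown. The illustrative rise in the 1B pass probability from 0.20 to 0.42 or 0.75 rests on the assumptions in Step 4 and should not be read as an expected effect. The stated sample size and test are unaffected. The change is worth making because it is nearly free and success allows only one failure in 56. The documents do not support a claim that the results will be biased.

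**What to change.** In Section 7.2, complete eligibility checks, skin assessment and skin preparation at all ten electrode sites before the electrode age is known, following the same application note for every participant.

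In Section 6.5.2, replace visibility upon enrollment with release of the assignment only after staff confirm in the database that preparation is done. State that no further preparation is given for the assigned set once its age is known.

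The cost is a slightly changed visit sequence, one confirmation field and protocol wording. Staff, sample size and analysis stay the same. Staff will still know the electrode age at placement and at the swap decision, so the change closes the preparation route only.

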#### 3.1 Endpoints

##### 3.1.1 Primary Endpoints

Validation

- Number of failures of ‘unable to obtain a 12-lead ECG’ with the Philips HeartStart Intrepid Monitor/Defibrillator
- Number of diagnostic quality 12-lead ECG tracings from the Philips HeartStart Intrepid Monitor/Defibrillator

Safety

- Frequency and severity of unexpected adverse events
- Unanticipated adverse device effects (UADE)

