#### 3.2 Hypotheses

Hypothesis 1A: We hypothesize that a 12-lead ECG will be obtained greater than 90% of the time with a target goal of 99%.

$$H_{0A}: \pi_A \leq 0.90$$

$$H_{1A}: \pi_A > 0.90$$

Document ID:	CC_TC_ECR_Intrepid 12Lead_2022_11549	Document title: Philips HeartStart Intrepid 12-lead ECG Study – The ICE study Protocol	Classification:	For internal use
Modified:	12SEP2022		Clinical Protocol	Author:
Version:	2.0	Approver:		Ref to Page 2
Status:	Final	Page:		23 of 51

Hypothesis 1B: We hypothesize that 12-lead ECG tracings will be of diagnostic quality greater than 90% of the time with a target goal of 99%.

$$H_{0B}: \pi_B \leq 0.90$$

$$H_{1B}: \pi_B > 0.90$$

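### The only stated Fail rule applies after dried electrodes are swapped for new ones, and endpoint 1A does not say which result counts, so 1A could pass while the update performs poorly at high impedance

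*Combined protocol and SAP*

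**What the plan says.** Sections 3 and 5.1 give the purpose: to validate the device after a software change made for high impedance. Section 6.1 randomises participants to electrodes that are new, 24 hours open or 30 days open, and explains that "The dried electrodes will be used to simulate high impedance".

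Section 7.2 sets out what happens at the preview screen. "If the 12-lead ECG cannot be obtained and the participant has been randomized to either the 1 day or 30 day electrodes", then "the electrodes will be swapped for electrodes from an unopened package". It continues: "If the 12-lead ECG cannot be obtained after the electrodes have been changed, this will be considered a 'Fail". It states no Fail rule for participants randomised to new electrodes, who have no swap, and gives no label to the failure before the swap.

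The endpoint text is shorter. Section 3.1.1 counts failures described as "unable to obtain a 12-lead ECG", and Section 10.4.2 has only "Endpoint 1A: Obtaining the 12-lead ECG". Neither refers to the Fail rule in Section 7.2, the swap or the electrode set. Section 3.2 tests a 90% null with a 99% target and names no electrode condition. Both 1A and 1B must be met for study success.

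**The concern.** Endpoint 1A has two possible scorings, and the only explicit scoring text supports the one that takes away the tested condition. Under that scoring, a dried-electrode attempt that fails and is rescued by new electrodes counts as a success. 1A then measures whether an ECG was obtained with a permitted electrode change, whereas the objective concerns the update at high impedance.

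No other part of the plan recovers the result before the swap:

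- **Endpoint 1B.** Section 6.1 says that no recording can be obtained without a good signal. A failed dried-electrode attempt therefore leaves no tracing to grade, and any tracing graded after a swap comes from new electrodes.
- **Device deficiency log (Section 8.6).** It may record such an event but is not linked to 1A.
- **Check after the first three participants (Sections 10.5 and 10.6).** It does not say whether it is judged before or after a swap.
- **Other analyses.** Sections 10.4.4 and 10.4.5 plan no exploratory or sensitivity analyses. No analysis of swaps, or by electrode age, is specified.

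Section 4.2 says the study is needed to confirm function before the software is released. Success could be declared although the update performs poorly in the condition it was written for.

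**Working it through.** **Inputs from the documents.** Null 0.90 and target 0.99 (Sections 3.2 and 10.1); one-sided exact binomial test at 0.025, 80% power, 56 evaluable participants (Sections 10.1 and 10.4.2); balanced blocks over three electrode ages (Section 6.5.1).

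**Assumptions not in the documents.** One result per participant, although three ECGs are taken; 19 new, 19 at 24 hours and 18 at 30 days, so 37 on dried electrodes; 99% success on new electrodes; independent participants.

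**The plan's own figure.** The normal approximation gives ((1.96·√0.09 + 0.842·√0.0099)/0.09)² = 55.7, so 56. For the exact test at n = 56:

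- P(X ≥ 55 | 0.90) = 0.0198
- P(X ≥ 54 | 0.90) = 0.0719

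Passing therefore needs at least 55 of 56, that is, at most one failure. Power at 0.99 is 0.892.

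**Model.** Let p be success on dried electrodes as randomised, f the share of dried-electrode failures seen at preview (and so eligible for the swap), and s the success rate after the swap. Scored after the swap, a dried-electrode participant succeeds with probability p + (1 − p)·f·s. The chance of passing is the probability of at most one failure among 19 participants at 0.99 and 37 at that rate.

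**Case 1: true rate on randomised electrodes exactly at the null, f = 1.** p = (0.90 × 56 − 19 × 0.99)/37 = (50.40 − 18.81)/37 = 0.854.

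| Scoring of 1A | Dried-electrode success as scored | Chance 1A passes |
|---|---|---|
| Randomised electrodes | 0.854 | 0.018 |
| After swap, s = 0.99 | 0.9985 | 0.975 |
| After swap, s = 0.95 | 0.993 | 0.922 |
| After swap, s = 0.90 | 0.985 | 0.834 |
| After swap, s = 0.50 | 0.927 | 0.205 |

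The chance reaches 0.025 when f·s = 0.063, that is, when about 6.3% of dried-electrode failures are rescued.

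**Case 2: as Case 1 with s = 0.95, but some failures appear only at the later recordings.** Section 7.2 describes no swap at minutes 1, 6 and 11.

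| Share of failures seen at preview (f) | Chance 1A passes |
|---|---|
| 0.75 | 0.475 |
| 0.50 | 0.184 |
| 0.25 | 0.061 |
| 0.10 | 0.030 |

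**Case 3: stress case, dried electrodes never work (p = 0, f = 1).** The chance of passing is 0.89, 0.39 or 0.09 at s = 0.99, 0.95 or 0.90, against essentially 0 when scored on the randomised electrodes.

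**Power if 1A is scored on the randomised electrodes (n = 56, new at 0.99).**

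| Success on dried electrodes | Power for 1A |
|---|---|
| 0.99 | 0.89 |
| 0.98 | 0.76 |
| 0.97 | 0.63 |
| 0.95 | 0.39 |

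Power of 80% needs about 98.3% success on dried electrodes.

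**The case against.** The strongest reply is that the harmful reading is not established. Nothing ties the Fail in Section 7.2 to endpoint 1A; it may only label the end of a preview step. Participants on new electrodes have to be scored from the endpoint's own words, and those words would equally cover a dried-electrode failure before the swap. This stands: the endpoint is undefined, and the documents do not contradict themselves. It does not remove the problem, because a confirmatory endpoint should not be left to be settled after results are seen.

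A second reply is that the null names no electrode condition, electrode age is only a balancing factor, and scoring as randomised would still pool about one third new electrodes. Wet skin, also named in Section 5.1, may survive a swap, so a failure after the swap still carries information. Each of these is true. The exact test does keep its level for whatever quantity is scored. None of them restores the dried-electrode failures that the swap removes.

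A third reply is that the figures depend on unknown inputs: Cases 1 and 2 span 0.018 to 0.975. That also stands. If failures share a cause that new electrodes do not fix, s is low and the gap shrinks. The figures show what the rule permits; they do not predict the result. The data may also exist: assignment is held in the database and device data are downloaded daily. The CRF is not among the documents, so whether swaps are recorded is unknown.

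**Conclusion.** The concern holds and should be resolved before data collection. The plan does not define which result 1A scores, and reading it by the only stated Fail rule discards dried-electrode failures that new electrodes resolve. On that reading, and with the assumptions above, the chance of passing 1A at a true randomised-electrode rate of 90% rises from 0.018 to between 0.205 and 0.975 for swap success from 50% to 99%, if all failures are seen at preview. If only 10% are seen there, with 95% swap success, it is 0.030, close to the nominal 0.025. Confidence is high that the endpoint is undefined; how much it matters in practice depends on rates the documents do not give.

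**What to change.** **Preferred change.**

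- In Sections 7.2 and 10.4.2, define 1A as a 12-lead ECG obtained on the randomised electrodes without a swap, and state the same Fail rule for participants on new electrodes.
- Keep the swap as an operational step. Record the result before it, and the swap itself, in a CRF field if the CRF does not already hold them.
- Report success before and after the swap by electrode age, with the 95% Clopper-Pearson interval already named in Section 10.2.
- In Sections 10.5 and 10.6, state that the check on the first three participants uses the result before any swap.
- For 1B, flag tracings taken after a swap and report 1B by the electrodes actually used.
- In Section 10.1, say that the 99% planning rate refers to the randomised electrodes, and restate the power.

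**Minimum, if the sponsor keeps the result after the swap as 1A.** Say so in Sections 3.1.1 and 10.4.2, report success before the swap by electrode age, and limit the conclusion to an ECG obtained with a permitted electrode change.

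**Cost.** Protocol and SAP wording and at most one CRF field, with no added visits or procedures. The downside is lower power for 1A if dried electrodes fall short of 99%, as tabulated above. At the plan's own 99%, 56 participants remain enough. For planning only, the first sample size to reach 80% power is about 70, 85 or 127 at 98%, 97% or 95% on dried electrodes. The last is not stable, because power dips below 80% again at 131 to 140. The request is to restate the power, not to change the sample size.
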